### 9.7.1 Main analysis

All outcome events are based on reported AE data which will be handled according to BI standards (see the section below).

[figure not shown]
The safety analysis will include all patients who registered, received the Prizbind® for Intravenous Solution 2.5 g treatment and collected CRF except for who meet the ineligible criteria (see Section 9.7).

[figure not shown]
AEs will be coded using the current version of the Medical Dictionary for Regulatory Activities (MedDRA). Based on the concept of treatment emergent AEs, all AEs occurring between first intake of Prizbind® for Intravenous Solution 2.5 g prescribed at baseline visit up to 5 days after the last intake will be considered 'treatment period'. In addition, AEs with onset date before start of the trial treatment but with worsening in intensity during the treatment will also be assigned to the on-treatment period. Other AEs will be assigned to the screening or post-treatment period, respectively.

An AE is considered to be an ADR if either the physician who has reported the AE or the sponsor assesses its causal relationship as 'related'.

The frequency and percentages of ADRs, SAEs, and other AEs occurred in treatment period as well as treatment + post-treatment period will be tabulated by system organ class and preferred term for all patients and for subgroups based on the important baseline characteristics (details will be described in the TSAP).

No imputation is planned for missing AE data except for missing onset dates which will be handled according to BI standard.

## **9.8            QUALITY CONTROL**

All processes are conducted according to GPSP SOPs <102-MLS-90-119>. Appropriate records and documents are stored based on the GPSP SOPs and these processes are checked by internal self-check.

## **9.9            LIMITATIONS OF THE RESEARCH METHODS**

The general scientific objective of this non-interventional study is to obtain an estimate of the occurrence of the adverse events in the population under study. Due to the nature of a single cohort observational study, however, there are issues that may impose limitations in particular on the validity of the assessment based on the study data such as selection bias, loss to follow up, channeling bias and information and recall bias. Thus, comparisons and causal conclusions cannot be made, except for the investigator reported drug-related AEs. For patients enrolled in sites with the contract implemented after administration of Prizbind the information is limited to the information included in the medical chart which might lead to missing information.

## **9.10          OTHER ASPECTS**

### **9.10.1       Data quality assurance**

This PMS is to be conducted in accordance with both the in-house PMS SOP and working instructions which are in compliance with GPSP.

### **9.10.2       Study records**

Paper CRFs for individual patients will be provided by the sponsor.

#### 9.10.2.1 Source documents

Source documents provide evidence for the existence of the patient and substantiate the integrity of the data collected. Source documents are filed at the investigator's site.

Data entered in the CRFs that are transcribed from source documents must be consistent with the source documents or the discrepancies must be explained. The investigator may need to request previous medical records or transfer records, depending on the study; also current medical records must be available. For CRFs, all data must be derived from source documents.

#### 9.10.2.2 Direct access to source data and documents

Direct access to source data and documents for PMS is not allowed in Japan.

## **10. PROTECTION OF HUMAN SUBJECTS**

The study will be carried out in compliance with the protocol, the principles laid down in the Declaration of Helsinki, in accordance with the ICH Harmonised Tripartite Guideline for Good Clinical Practice (GCP) (to the extent applicable to the NIS setting and required by local regulations), Good Epidemiological Practice (GEP), Guidelines for Good Pharmacoepidemiology Practice (GPP), and relevant BI Standard Operating Procedures (SOPs). Standard medical care (prophylactic, diagnostic and therapeutic procedures) remains in the responsibility of the treating physician of the patient.

The investigator should inform the sponsor immediately of any urgent safety measures taken to protect the study subjects against any immediate hazard, and also of any serious breaches of the protocol.

### **10.1 STUDY APPROVAL, PATIENT INFORMATION, AND INFORMED CONSENT**

The review by Institutional Review Board (IRB) is not mandatory for conducting the PMS in Japanese GPSP. The sponsor will enter into a contract with a representative (i.e., head of hospital) in accordance with GPSP. Written informed consent prior to patient participation in the trial is not a regulatory or legal requirement in accordance with GPSP.

### **10.2 STATEMENT OF CONFIDENTIALITY**

Individual patient medical information obtained as a result of this study is considered confidential and disclosure to third parties is prohibited with the exceptions noted below. Patient confidentiality will be ensured by using patient identification code numbers.

Treatment data may be given to the patient's personal physician or to other appropriate medical personnel responsible for the patient's welfare. Data generated as a result of the study need to be available for inspection on request by the participating physicians, the sponsor's representatives by the regulatory authorities.

## 11. MANAGEMENT AND REPORTING OF ADVERSE EVENTS/ADVERSE REACTIONS

### 11.1 DEFINITIONS OF ADVERSE EVENTS

#### Adverse event

An adverse event (AE) is defined as any untoward medical occurrence in a patient or clinical investigation subject administered a medicinal product and which does not necessarily have a causal relationship with this treatment. An adverse event can therefore be any unfavourable and unintended sign (e.g. an abnormal laboratory finding), symptom, or disease temporally associated with the use of a medicinal product, whether or not considered related to the medicinal product.

#### Adverse reaction

An adverse reaction is defined as a response to a medicinal product which is noxious and unintended. Response in this context means that a causal relationship between a medicinal product and an adverse event is at least a reasonable possibility. Adverse reactions may arise from use of the product within or outside the terms of the marketing authorisation or from occupational exposure. Conditions of use outside the marketing authorization include off-label use, overdose, misuse, abuse and medication errors.

#### Serious adverse event

A serious adverse event is defined as any AE which

- results in death,
- is life-threatening,
- requires in-patient hospitalization, or
- prolongation of existing hospitalisation,
- results in persistent or significant disability or incapacity, or
- is a congenital anomaly/birth defect

Life-threatening in this context refers to a reaction in which the patient was at risk of death at the time of the reaction; it does not refer to a reaction that hypothetically might have caused death if more severe.

Medical and scientific judgement should be exercised in deciding whether other situations should be considered serious reactions, such as important medical events that might not be immediately life threatening or result in death or hospitalisation but might jeopardise the patient or might require intervention to prevent one of the other outcomes listed above.

Examples of such events are intensive treatment in an emergency room or at home for allergic bronchospasm, blood dyscrasias or convulsions that do not result in hospitalisation or development of dependency or abuse. Any suspected transmission via a medicinal product of an infectious agent is also considered a serious adverse reaction.

An AE which possibly leads to disability will be reported as an SAE.

#### Adverse Event of Special Interest (AESI)

The term AESI relates to any specific AE that has been identified at the project level as being of particular concern for prospective safety monitoring and safety assessment within this

study, e.g. the potential for AEs based on knowledge from other compounds in the same class.

No AESIs have been defined for this study.

## 11.2 ADVERSE EVENT AND SERIOUS ADVERSE EVENT COLLECTION AND REPORTING

The investigator shall maintain and keep detailed records of all AEs in their patient files.

### Collection of AEs

The study design is of non-interventional nature and the study is conducted within the conditions of the approved marketing authorisation. Sufficient data from controlled interventional trials are available to support the evidence on the safety and efficacy of the studied BI drug. For this reason the following AE collection and reporting requirements have been defined.

The following must be collected by the investigator in the CRF:

- all adverse drug reaction (ADRs) (serious and non-serious),
- all AEs with fatal outcome,

All ADRs including those persisting after study completion must be followed up until they are resolved, have been sufficiently characterized, or no further information can be obtained.

The investigator carefully assesses whether an AE constitutes an ADR using the information below.

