Population:	
Inclusion criteria
 
 
- Patients who are prescribed with Prizbind® for Intravenous Solution 2.5 g by the discretion of investigators
 
 
Exclusion criteria
 
 
- None
 
		

[figure not shown]
Name of company: Boehringer Ingelheim			
Name of finished medicinal product: Prizbind® for Intravenous Solution 2.5 g			
Name of active ingredient: Idarucizumab (V03AB37)			
Protocol date: 23 Sep 2016	Study number: 1321.15	Version/Revision: 3.0	Version/Revision date: 25 Mar 2019
Variables:	Primary outcomes Any suspected ADRs (primary outcome), Serious AEs, and AEs for important potential risks(hypersensitivity, thrombotic event) Secondary outcomes Effectiveness will be assessed with a focus on the following variable as secondary outcome. Reversal of anticoagulation as measured by coagulation test (aPTT, activated partial thromboplastin time)(secondary outcome) 		
Data sources:	Case Report Forms (CRFs) for individual patients will be provided by the sponsor. After the medical examination and observation at the specified points (Baseline, up to Week 4, or discontinuation) are completed, the investigator needs to immediately enter data of the registered patients (including withdrawals and dropouts) in CRF. In case that any adverse events occur, the data should be as soon as possible entered into CRF.		
Study size:	300		
Data analysis:	Due to the nature of the observational study, no confirmatory statistical testing is foreseen in this study. Analyses are descriptive in nature including means, standard deviation, min, Q1, medians, Q3, max, frequency and percentages.		
Milestones:	Start of data collection: 28 September 2016 End of data collection: March 2020 (in plan) Final report of study results: 4Q 2020 (in plan)		

Table 1 Flow chart

Observation / Evaluation time points are approximate. Collected data should be reported as those to the closest available time.

Item	Time	Observation period			
		Baseline before treatment	Drug administration	48 hours after administration	4 weeks/or discontinuation
Patient registration* 	X				
Patient demographics	X				
Medical history	X				
Dabigatran use	X				
Bleed assessment Surgery/Procedure		X (to be reported throughout the observation period)			
Prizbind® administration		X			

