### 9.3.2 Outcomes

#### 9.3.2.1 Primary outcomes

Safety will be assessed with a focus on the following variables, frequencies and percentages.

- Any suspected ADRs (primary outcome)
- Serious AEs
- AEs for important potential risks\*: hypersensitivity, thrombotic event (ischemic stroke, myocardial infarction, pulmonary embolism, deep vein thrombosis, systemic embolism) \*: Immunogenicity will be assessed by clinical signs and symptoms of hypersensitivity.

How to assess and report AEs including the definitions are described in section 11.

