## 9.4 DATA SOURCES

Case Report Forms (CRFs) for individual patients will be provided by the sponsor.

After the medical examination and observation at the specified points (Baseline, up to 4 weeks, or discontinuation) are completed, the investigator needs to immediately enter data of the registered patients (including withdrawals and dropouts) in CRF. In case that any adverse events occur, the data should be immediately entered into CRF.

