#### Information required

For each reportable adverse event, the investigator should provide the information requested on the appropriate CRF pages.

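### Protocol 11.2 requires only ADRs and fatal AEs on the CRF, while 9.4 and the abstract ask for any AE; SAE and thrombotic/hypersensitivity tables are incomplete wherever sites followed 11.2

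*Protocol*

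**What the plan says.** **The narrow rule.** Protocol 11.2 (Collection of AEs) names two categories that must be collected in the CRF: "all adverse drug reaction (ADRs) (serious and non-serious") and "all AEs with fatal outcome". It justifies this by the controlled-trial evidence already available. Section 11.2 also says "The investigator shall maintain and keep detailed records of all AEs in their patient files", and under Information required: "For each reportable adverse event, the investigator should provide the information requested on the appropriate CRF pages".

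**The wide rule.** Protocol 9.4 says "In case that any adverse events occur, the data should be immediately entered into CRF". The abstract (Data sources) says "In case that any adverse events occur, the data should be as soon as possible entered into CRF". The adverse-event row of Table 1 runs through the whole period and is not limited to ADRs or deaths, although it does not use the word any.

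**What is to be analysed.** Protocol 9.3.2.1 lists suspected ADRs, serious AEs, and AEs of hypersensitivity and "thrombotic event (ischemic stroke, myocardial infarction, pulmonary embolism, deep vein thrombosis, systemic embolism"). The last two groups have no causality condition. The same section then states: "How to assess and report AEs including the definitions are described in section 11". Protocol 9.7.1 tabulates ADRs, SAEs and other AEs. SAP 7.8.1 tabulates ADRs, AEs, SAEs and the important identified and potential risks, and plans subgroup odds ratios with exact intervals for ADRs, SAEs, serious ADRs and the important potential risks. Protocol 9.5 treats thrombosis and hypersensitivity as the key survey items and bases the precision argument for 300 patients on them.

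**The concern.** A site reading section 11 as the governing text, which is where 9.3.2.1 sends it, need not enter a non-fatal stroke, deep vein thrombosis or hypersensitivity event that the investigator considers unrelated. Tables titled AE, SAE or thrombotic event would then hold only events that were judged related or were fatal.

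The protocol describes no direct way for the sponsor to find the missing events. Monitoring does not apply (9.6), direct source access is not allowed (9.10.2.2), and no AESIs are defined (11.1).

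Three things are at stake:

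- The percentages for SAEs and the key risks would be biased downward.
- If sites differed in the rule they followed, the tables would mix two definitions, and subgroup odds ratios could be biased in either direction.
- The reader would not be told. Section 9.9 ties missing information only to sites contracted after administration, and SAP section 4 reports no change to the planned analysis.

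The suspected-ADR outcome is largely protected. An event counts as an ADR if either the physician or the sponsor judges it related (Protocol 9.7.1, SAP 7.8.1). The only loss there is a non-fatal event that the investigator judged unrelated, that never reached the CRF, and that the sponsor might have judged related.

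**Working it through.** **1. Which events each rule requires**

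| Event | Protocol 11.2 | Protocol 9.4 and abstract | Needed for planned tables |
|---|---|---|---|
| ADR, serious or not | Yes | Yes | Yes |
| Fatal AE, any causality | Yes | Yes | Yes |
| Non-fatal SAE, investigator says unrelated | Not required | Yes | Yes (SAE tables) |
| Non-fatal thrombotic or hypersensitivity AE, investigator says unrelated | Not required | Yes | Yes (risk tables) |
| Other non-fatal, non-serious AE, investigator says unrelated | Not required | Yes | Yes (overall AE tables) |

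The last three rows are the gap.

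**2. Reproducing the plan's own figures**

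Inputs from Protocol 9.5: N = 300; planning rates 5.3% (thrombosis) and 12.3% (hypersensitivity). Method: Clopper-Pearson 95% interval with x = N × rate, allowing fractional x. The lower limit is the 2.5% quantile of Beta(x, N − x + 1); the upper limit is the 97.5% quantile of Beta(x + 1, N − x).

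- Thrombosis: x = 300 × 0.053 = 15.9, giving 3.05% to 8.48%. Table 2 has 3.0% to 8.5%.
- Hypersensitivity: x = 300 × 0.123 = 36.9, giving 8.81% to 16.56%. Table 2 has 8.8% to 16.6%.

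The sample-size figures reproduce and are not in dispute. They hold if all such events reach the CRF.

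**3. If only ADRs and fatal AEs are entered**

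Let c be the share of true events judged related by the investigator or fatal. The documents do not give c, so the values below are assumptions. Expected observed rate = c × true rate; x = 300 × c × true rate.

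| Event (true rate) | c | x | Observed rate | 95% CI |
|---|---|---|---|---|
| Thrombosis (5.3%) | 0.75 | 11.9 | 4.0% | 2.1 to 6.9 |
| | 0.50 | 8.0 | 2.7% | 1.1 to 5.2 |
| | 0.25 | 4.0 | 1.3% | 0.4 to 3.4 |
| Hypersensitivity (12.3%) | 0.75 | 27.7 | 9.2% | 6.2 to 13.1 |
| | 0.50 | 18.4 | 6.2% | 3.7 to 9.5 |
| | 0.25 | 9.2 | 3.1% | 1.4 to 5.7 |

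Solving for the c at which the upper limit equals the true rate gives about 0.52 for thrombosis and about 0.69 for hypersensitivity. Below those values the interval excludes the true rate; at c = 0.75 it still contains it.

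**4. Subgroup odds ratios**

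Assume a true thrombosis rate of 5.3% in both subgroups, with capture of 0.75 in one and 0.50 in the other. The observed rates are 0.053 × 0.75 = 0.03975 and 0.053 × 0.50 = 0.0265. The expected odds ratio is (0.03975 / 0.96025) / (0.0265 / 0.9735) = 1.52, where the true value is 1.

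**The case against.** **Section 11.2 can be read as a minimum.** It says what must be collected and does not bar other events, and 9.4 then adds any AE. A later sentence in 11.2, about patients treated after 15 April 2019, refers to AEs rather than ADRs no longer being collected in the CRF, which suggests that AEs had been collected until then. The analysis sections also presuppose wider collection. This makes the loss less certain. But 11.2 gives a reason for defining its own requirements, and 9.3.2.1 defers to it. If it is only a minimum, practice is left to each site, so the conflict remains.

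**The sponsor is not wholly blind.** The CRF collects reasons for concomitant medication, blood products, restarted anticoagulants, laboratory values and D-dimer (Protocol 9.3.3). A treated thrombosis or allergic reaction might show there and prompt a query. That is fair, but it is indirect, and no such check is described.

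**The sizes are illustrative.** This stands. No capture fraction comes from the documents. The 12.3% may also not apply to the SAP's category, which is now an identified risk described as hypersensitivity (shock and anaphylaxis). The odds-ratio bias of 1.52 is small beside random error: with an assumed 150 patients per subgroup it corresponds to about 6 against 4 events, with an exact 95% interval of roughly 0.35 to 7.5.

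**Section 9.9 already carries caveats.** It names information bias in general and says that comparisons and causal conclusions cannot be made. It does not mention a restriction on which AEs were collected.

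**Conclusion.** The concern holds. The protocol contains two incompatible collection rules, and the narrower one does not support the SAE, overall AE and thrombotic/hypersensitivity tables that the protocol and SAP promise. This follows from the text and needs no assumption.

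Whether events were actually lost, and how many, depends on which rule sites followed and on the share of events judged related or fatal; the documents give neither. If all sites followed 9.4, there is no loss. If they followed 11.2, the bias in the percentages is downward, and with 300 patients it would push the interval below the planning rate once capture fell to about 52% (thrombosis) or 69% (hypersensitivity). The tables would be incomplete, not empty, because ADRs and fatal AEs are captured under either rule. The suspected-ADR outcome is mostly unaffected. The point should be fixed before the AE, SAE and risk tables are reported.

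**What to change.** Reconcile the abstract, Table 1 and sections 9.3.2.1, 9.4, 9.7.1 and 11.2 of the protocol with SAP 7.8.1, so that one AE collection rule applies.

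**If CRF collection is closed.** This is likely: CRFs cover patients treated up to 14 April 2019 (9.1), data collection was planned to end in March 2020 (section 6), and the SAP was revised in March 2021. State in the SAP and the report which rule sites followed. If it was 11.2, or a mixture:

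- retitle the AE, SAE and risk tables in SAP 7.8.1 as ADRs and fatal AEs, or footnote their percentages as minimum estimates;
- put the same note on the subgroup odds ratios for SAEs and the important potential risks;
- add the restriction to the limitations in 9.9.

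The cost is some titles or footnotes, one sentence in 9.9, and a more modest claim.

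**If collection is still open.** Make 11.2 require CRF entry of all serious AEs and all thrombotic and hypersensitivity AEs regardless of causality, in addition to ADRs and fatal AEs. If the overall AE tables are kept, they need either entry of every AE, as 9.4 says, or a title that shows the limit. The cost is a protocol wording change and the extra entries at sites.

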### Causal relationship of adverse event

The definition of an adverse reaction implies at least a reasonable possibility of a causal relationship between a suspected medicinal product and an adverse event. An adverse reaction, in contrast to an adverse event, is characterised by the fact that a causal relationship between a medicinal product and an occurrence is suspected.

Medical judgment should be used to determine the relationship, considering all relevant factors, including pattern of reaction, temporal relationship, de-challenge or re-challenge, confounding factors such as concomitant medication, concomitant diseases and relevant history.

Arguments that may suggest a **reasonable causal relationship** could be:

- The event is **consistent with the known pharmacology** of the drug
- The event is known to be caused by or **attributed to the drug class**.
- A **plausible time to onset of the event** relative to the time of drug exposure.
- Evidence that the **event is reproducible** when the drug is re-introduced
- **No medically sound alternative etiologies** that could explain the event (e.g. preexisting or concomitant diseases, or co-medications).
- The event is typically **drug-related and infrequent in the general population** not exposed to drugs (e.g. Stevens-Johnson syndrome).

- An indication of dose-response (i.e. greater effect size if the dose is increased, smaller effect size if dose is diminished).

Arguments that may suggest that there is **no reasonable possibility of a causal relationship** could be:

- No plausible time to onset of the event relative to the time of drug exposure is evident (e.g. pre-treatment cases, diagnosis of cancer or chronic disease within days/weeks of drug administration; an allergic reaction weeks after discontinuation of the drug concerned)
- Continuation of the event despite the withdrawal of the medication, taking into account the pharmacological properties of the compound (e.g. after 5 half-lives). Of note, this criterion may not be applicable to events whose time course is prolonged despite removing the original trigger.
- Additional arguments amongst those stated before, like alternative explanation (e.g. situations where other drugs or underlying diseases appear to provide a more likely explanation for the observed event than the drug concerned).
- Disappearance of the event even though the study drug treatment continues or remains unchanged.

